## GI Adverse Event Management Algorithm

Rule out non-inflammatory causes. If non-inflammatory cause is identified, treat accordingly and continue I-O therapy. Opiates/narcotics may mask symptoms of perforation. Infliximab should not be used in cases of perforation or sepsis.

[figure not shown]

Patients on IV steroids may be switched to an equivalent dose of oral corticosteroids (e.g. prednisone) at start of tapering or earlier, once sustained clinical improvement is observed. Lower bioavailability of oral corticosteroids should be taken into account when switching to the equivalent dose of oral corticosteroids.

27-Jun-2019

## Renal Adverse Event Management Algorithm

Rule out non-inflammatory causes. If non-inflammatory cause, treat accordingly and continue I-O therapy.

[figure not shown]

Patients on IV steroids may be switched to an equivalent dose of oral corticosteroids (e.g. prednisone) at start of tapering or earlier, once sustained clinical improvement is observed. Lower bioavailability of oral corticosteroids should be taken into account when switching to the equivalent dose of oral corticosteroids.

27-Jun-2019

## Pulmonary Adverse Event Management Algorithm

Rule out non-inflammatory causes. If non-inflammatory cause, treat accordingly and continue I-O therapy. Evaluate with imaging and pulmonary consultation.

[figure not shown]

Patients on IV steroids may be switched to an equivalent dose of oral corticosteroids (e.g. prednisone) at start of tapering or earlier, once sustained clinical improvement is observed. Lower bioavailability of oral corticosteroids should be taken into account when switching to the equivalent dose of oral corticosteroids

27-Jun-2019

## Hepatic Adverse Event Management Algorithm

Rule out non-inflammatory causes. If non-inflammatory cause, treat accordingly and continue I-O therapy. Consider imaging for obstruction.

[figure not shown]
Patients on IV steroids may be switched to an equivalent dose of oral corticosteroids (e.g. prednisone) at start of tapering or earlier, once sustained clinical improvement is observed. Lower bioavailability of oral corticosteroids should be taken into account when switching to the equivalent dose of oral corticosteroids.

\*The recommended starting dose for grade 4 hepatitis is 2 mg/kg/day methylprednisolone IV.

27-Jun-2019

## Endocrinopathy Adverse Event Management Algorithm

Rule out non-inflammatory causes. If non-inflammatory cause, treat accordingly and continue I-O therapy. Consider visual field testing, endocrinology consultation, and imaging.

[figure not shown]

Patients on IV steroids may be switched to an equivalent dose of oral corticosteroids (e.g. prednisone) at start of tapering or earlier, once sustained clinical improvement is observed. Lower bioavailability of oral corticosteroids should be taken into account when switching to the equivalent dose of oral corticosteroids.

27-Jun-2019

## Skin Adverse Event Management Algorithm

Rule out non-inflammatory causes. If non-inflammatory cause, treat accordingly and continue I-O therapy.

Patients on IV steroids may be switched to an equivalent dose of oral corticosteroids (e.g. prednisone) at start of tapering or earlier, once sustained clinical improvement is observed. Lower bioavailability of oral corticosteroids should be taken into account when switching to the equivalent dose of oral corticosteroids.

[figure not shown]
\*Refer to NCI CTCAE v4 for term-specific grading criteria.

^If SJS/TEN is suspected, withhold I-O therapy and refer patient for specialized care for assessment and treatment. If SJS or TEN is diagnosed, permanently discontinue I-O therapy.

27-Jun-2019

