##### **4.3.2 Dose Delay Criteria**

In some cases, the natural history of select AEs associated with immunotherapy can differ from and be more severe than AEs caused by other therapeutic classes. Early recognition and management may mitigate severe toxicity.

Guidance for Investigators is provided in the current BMS-986016 and BMS-936558 (nivolumab) IBs. Additionally, management algorithms have been developed to assist Investigators with select toxicities and can be found in the current BMS-936558 (nivolumab) IB; toxicities for which management algorithms have been developed include:

Pulmonary

Gastrointestinal

Hepatic

Endocrine

Renal

Dermatologic

Neurologic (see [Table 5.1-2](#) “Neurological Exam” for criteria for protocol-required neurologic exams)

Cardiac

Subjects who experience the following must have all study drug(s) held:

Potential DLTs (per definition, are related to study drug) until DLT relatedness is defined

Select drug-related AEs and drug-related laboratory abnormalities:

- $\geq$  Grade 1 pneumonitis
- $\geq$  Grade 1 myocarditis (see [Appendix 4](#))
- All troponin T or I elevations require a dose delay to allow for prompt cardiac and safety evaluation.
- $\geq$  Single grade increase shift from baseline (at least to Grade 2) of AST, ALT, and/or total bilirubin
- $\geq$  Grade 2 creatinine
- $\geq$  Grade 2 diarrhea or colitis
- $\geq$  Grade 2 neurological AE
- Grade 4 amylase and/or lipase abnormalities regardless of symptoms or clinical manifestations

AE, laboratory abnormality, or concurrent illness that, in the judgment of the Investigator, warrants delaying the dose of study drug.

Subjects may be dosed no less than 12 days in Q2W regimen and 25 days in Q4W from the previous dose and no more than 3 days from scheduled dose. If an infusion cannot be administered at a scheduled visit, it should be administered as soon as possible. Subsequent dosing visits will follow every 2 weeks or every 4 weeks after the delayed dose. A dose given more than 3 days after the intended dose date will be considered a delay. A maximum delay of 6 weeks between doses is allowed. Longer delays may be allowed following discussion with the Medical Monitor. Subjects who meet criteria listed in [Section 4.3.5](#) are required to permanently discontinue all study drug(s). All other subjects will be permitted to resume therapy with study drug(s) at the same dose level(s) following resolution of the AE as described in Section 4.3.3.

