#### **4.3.5 Guidelines for Permanent Discontinuation**

Subjects meeting any of the following criteria will be required to permanently discontinue all study drug(s) (BMS-986016 in Part A and Part A1; BMS-986016 and nivolumab [BMS-936558] or BMS-986213 in Parts B, C, D, and E):

Any  $\geq$  Grade 2 drug-related uveitis, eye pain, or blurred vision that does not respond to topical therapy and does not improve to Grade 1 severity within the retreatment period OR requires systemic treatment

Any  $\geq$  Grade 3 nonskin, drug-related AE lasting  $> 7$  days or recurs, with the following exceptions for laboratory abnormalities, drug-related uveitis, pneumonitis, bronchospasm, hypersensitivity reactions, infusion reactions, and endocrinopathies

Any  $\geq$  Grade 3 drug-related myocarditis, uveitis, pneumonitis, bronchospasm, or hypersensitivity reaction of any duration requires discontinuation.

Any  $\geq$  Grade 3 infusion reaction that does not return to Grade 1 in 6 hours or less requires discontinuation.

Any  $\geq$  Grade 3 drug-related endocrinopathies adequately controlled with only physiologic HRT do not require discontinuation.

Any  $\geq$  Grade 3 drug-related laboratory abnormalities do not require treatment discontinuation except:

- Any  $\geq$  Grade 3 drug-related thrombocytopenia  $> 7$  days or associated with bleeding requires discontinuation.
- AST, ALT, or bilirubin abnormalities that meet DLT criteria ([Section 3.1.2.6](#)) (In most cases of AST or ALT elevation meeting DLT criteria, study drugs will be permanently discontinued. If the Investigator determines a possible favorable benefit-risk ratio that warrants continuation of study drugs, a discussion between the Investigator and the BMS Medical Monitor/designee must occur.)
- Elevated troponin that meets DLT criteria ([Section 3.1.2.6](#))

Any Grade 4 drug-related AE or laboratory abnormality (including, but not limited to, creatinine, AST, ALT, or total bilirubin), except for the following events, which do **not** require discontinuation:

- Grade 4 neutropenia  $\leq$  7 days
- Grade 4 lymphopenia or leukopenia
- Isolated Grade 4 amylase or lipase abnormalities that are not associated with symptoms or clinical manifestations of pancreatitis
- Isolated Grade 4 electrolyte imbalances/abnormalities that are not associated with clinical sequelae and are corrected with supplementation/appropriate management within 72 hours of their onset

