- Grade 4 drug-related endocrinopathy AEs, such as adrenal insufficiency, adrenocorticotropic hormone deficiency, hyper- or hypothyroidism, or glucose intolerance, which resolve or are adequately controlled with physiologic HRT (corticosteroids, thyroid hormones) or glucose-controlling agents, respectively, may not require discontinuation after discussion with and approval from the BMS Medical Monitor.

Any event that leads to delay in dosing lasting  $>$  6 weeks from the previous dose requires discontinuation, with the following exceptions:

- Dosing delays to allow for prolonged steroid tapers to manage drug-related AEs are allowed. Prior to reinitiating treatment in a subject with a dosing delay lasting  $>$  6 weeks from the previous dose, the BMS Medical Monitor must be consulted. Tumor assessments should continue as per protocol even if dosing is delayed. Periodic study visits to assess safety and laboratory studies should also continue every 6 weeks or more frequently if clinically indicated during such dosing delays.
- Dosing delays lasting  $>$  6 weeks from the previous dose that occur for nondrug-related reasons may be allowed if approved by the BMS Medical Monitor. Prior to reinitiating treatment in a subject with a dosing delay lasting  $>$  6 weeks, the BMS Medical Monitor must be consulted. Tumor assessments should continue as per protocol even if dosing is delayed. Periodic study visits to assess safety and laboratory studies should also continue every 6 weeks or more frequently if clinically indicated during such dosing delays.

Any AE, laboratory abnormality, or intercurrent illness which, in the judgment of the Investigator, presents a substantial clinical risk to the subject with continued nivolumab dosing.

The consideration to reinitiate study therapy in selected cases at any time point after discontinuation could be made on a case-by-case basis after considering the overall benefit-risk profile and in consultation between the Investigator and the study Sponsor. The selected subjects will need to meet eligibility criteria. The original dose and schedule and protocol rules would apply accordingly ([Section 3.1.2.5](#)).

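### Section 4.3.5 does not require a permanent stop when drug-related SJS/TEN below Grade 4 is diagnosed, although the Appendix 4 guidance says to stop

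*Combined protocol and SAP*

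**What the plan says.** Appendix 4 (Skin Adverse Event Management Algorithm) says to withhold therapy and refer the patient if SJS/TEN is suspected. On diagnosis it says: "If SJS or TEN is diagnosed, permanently discontinue I-O therapy". The introduction to Appendix 4 describes all the algorithms as guidance to the investigator, which discussion with the Medical Monitor may supplement.

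Section 4.3.5 is worded as a requirement. The criteria that bear on this event are:

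- a general criterion for events of at least "Grade 3 nonskin, drug-related AE lasting" more than 7 days, or recurring;
- a short list of drug-related Grade 3 or higher events, ending with "hypersensitivity reaction of any duration requires discontinuation";
- "Any Grade 4 drug-related AE or laboratory abnormality", with listed exceptions, none of which concerns skin;
- a dosing delay of more than 6 weeks from the previous dose, with exceptions, one of which reads "Dosing delays to allow for prolonged steroid tapers to manage drug-related AEs are allowed";
- any event that, in the investigator's judgment, "presents a substantial clinical risk to the subject with continued nivolumab dosing".

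Section 4.3.2 says of subjects who do not meet Section 4.3.5: "All other subjects will be permitted to resume therapy with study drug(s) at the same dose level(s) following resolution of the AE". Section 4.3.3 sets the conditions for resuming: resolution to Grade 1 or baseline, normally within 6 weeks of the last dose. None of its exceptions concerns SJS/TEN.

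The closing paragraph of Section 4.3.5 allows study therapy to be restarted case by case after discontinuation, in consultation with the sponsor, if the subject meets the eligibility criteria.

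**The concern.** The appendix acts on the diagnosis, whereas the binding list acts on grade, organ class, duration or judgment. The one general criterion that would catch a prolonged or recurrent Grade 3 toxicity in most other organs leaves out skin. A site working only from the dosing rules could diagnose SJS/TEN, see it resolve, find no criterion met, and have permission to give the same dose again.

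What is at stake is re-exposure after a potentially severe skin reaction. The question is still live although enrollment closed on 30-Jul-2021. Section 3.1 lets treatment continue beyond 5 years, and Amendment 15 (16-Feb-2024) provides for participants who remain on treatment.

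**Working it through.** No formula applies, and the plan gives no figure to reproduce. The check takes drug-related SJS/TEN below Grade 4 through each criterion in Section 4.3.5 and asks whether the diagnosis itself forces a stop.

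| Section 4.3.5 criterion | Reaches the event? | Forced by the diagnosis? |
|---|---|---|
| Eye events | No | No |
| General Grade 3 or higher, over 7 days or recurrent | No, nonskin only | No |
| Named Grade 3 or higher events, any duration | Only if classified as a hypersensitivity reaction, and only at Grade 3 | No |
| Infusion reaction, endocrinopathy, laboratory criteria | No | No |
| Grade 4 | Outside by definition | No |
| Delay over 6 weeks | Only if the delay lasts that long and no exception applies | No |
| Investigator judgment of substantial risk | Only if so judged | No |

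Section 3.5 does not change this. It refers adverse events back to Section 4.3.5, and its separate item on clinical deterioration again rests on the investigator's assessment.

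**Whether the drug is held.** Section 3.1.3 makes nearly every drug-related Grade 3 or higher nonhepatic, nonhematologic toxicity a DLT. Grade 3 rash is exempt only if it improves to Grade 1 within 2 weeks, does not limit self-care and is not associated with infection. Section 4.3.2 requires all study drug to be held for a potential DLT. Most drug-related Grade 3 cases would therefore be held. Below Grade 3, the Section 4.3.2 list names no skin event, and the hold rests on its investigator-judgment item. A hold is not a permanent stop, and it leads into the resumption rules.

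**How much room the 6-week rule leaves.** The delay is counted from the previous dose. For Q4W dosing, 42 − 28 = 14 days past the due dose; for Q2W dosing, 42 − 14 = 28 days. A case resolving within that time can resume without the Medical Monitor being involved under this rule. Beyond it, the exceptions in Sections 4.3.3 and 4.3.5 require Medical Monitor consultation or approval.

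**Whether the rules lead to Appendix 4.** Section 3.4.4 on infusion reactions refers to Appendix 4 for the full set of algorithms, and the hold list cites it for myocarditis. Sections 4.3.3 and 4.3.5 do not cite it. Section 4.3.2 places the dermatologic algorithm in the nivolumab Investigator Brochure.

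**The case against.** The best case against is that the protocol already contains the instruction. Appendix 4 is part of the document that sites must follow. A specific direction to stop does not contradict a general permission to resume, and a site that obeys Appendix 4 breaks no rule. Section 4.3.2 also sends investigators to a dermatologic algorithm in the Investigator Brochure, which is not available here and may carry the same instruction. To resume, an investigator would have to diagnose SJS/TEN, not class it as Grade 3 hypersensitivity, judge continued dosing not to be a substantial risk, and set the appendix aside.

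Much of this stands. It makes a wrongful resumption unlikely, and it means the protocol never directs re-dosing. It does not close the gap: the appendix calls itself guidance, and the rules that decide resumption and discontinuation neither repeat the instruction nor cite it. Myocarditis shows the alternative, since it is cross-referenced in the hold list and named in Section 4.3.5.

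The case against is also right that the affected set is assumed. If every drug-related case were Grade 4, no subject would be affected. The skin figure is not shown either, so the absence of a grade threshold is read from the footnote text alone.

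**Conclusion.** The point holds as a safety inconsistency between a mandatory list and the protocol's own guidance. It rests on two assumptions: that drug-related SJS/TEN can be graded below 4, and that the Appendix 4 footnote applies whatever the grade. Its size cannot be calculated, because the documents give neither an incidence nor the number of subjects still exposed; events are probably rare. No effect on any endpoint follows.

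A reader might infer more than the documents support:

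- *That nothing stops or holds the drug.* A drug-related Grade 4 case is a mandatory stop, and most drug-related Grade 3 cases would be held as potential DLTs. The gap lies mainly in the permanent stop.
- *That resumption after a hold is the only way back to treatment for a subject who discontinues after Amendment 14.* Section 3.1.2.4 closes rechallenge to such subjects, but the closing paragraph of Section 4.3.5 still allows case-by-case reinitiation.
- *That the enrollment or rechallenge calendar measures the problem.* Those dates show who might still be treated. They say nothing about how often SJS/TEN occurs or how often treatment would be resumed after it.

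**What to change.** In Section 4.3.5, add diagnosed SJS or TEN of any grade to the permanent-discontinuation list, with a cross-reference to Appendix 4. State there that the closing reinitiation paragraph does not apply to these subjects.

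As a minor clarification, add suspected SJS/TEN to the hold list in Section 4.3.2, also citing Appendix 4. This helps mainly below Grade 3, where no potential-DLT hold would normally apply.

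The cost is two list lines, one sentence and the cross-references, with no added visits, procedures or data. The list lines make binding what the sponsor already advises, and the reinitiation sentence keeps that stop permanent.

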## Neurological Adverse Event Management Algorithm

[figure not shown]
Rule out non-inflammatory causes. If non-inflammatory cause, treat accordingly and continue I-O therapy.

Patients on IV steroids may be switched to an equivalent dose of oral corticosteroids (e.g. prednisone) at start of tapering or earlier, once sustained clinical improvement is observed. Lower bioavailability of oral corticosteroids should be taken into account when switching to the equivalent dose of oral corticosteroids.

27-Jun-2019

## Myocarditis Adverse Event Management Algorithm

Patients on IV steroids may be switched to an equivalent dose of oral corticosteroids (eg, prednisone) at start of tapering or earlier, once sustained clinical improvement is observed. Lower bioavailability of oral corticosteroids should be taken into account when switching to the equivalent dose of oral corticosteroids.

Prophylactic antibiotics should be considered in the setting of ongoing immunosuppression.

ATG = anti-thymocyte globulin; BNP = B-type natriuretic peptide; ECG = electrocardiogram; IV = intravenous; MRI = magnetic resonance imaging

27-Jun-2019

## APPENDIX 5 MEDDRA ANAPHYLACTIC REACTIONS

### Preferred Terms Included in the MedDRA Anaphylactic Reaction SMQ - Broad and Narrow Scopes

Preferred Term	Term Scope a
Acute respiratory failure	Broad Scope
Allergic oedema	Broad Scope
Anaphylactic reaction	Narrow Scope
Anaphylactic shock	Narrow Scope
Anaphylactic transfusion reaction	Narrow Scope
Anaphylactoid reaction	Narrow Scope
Anaphylactoid shock	Narrow Scope
Angioedema	Broad Scope
Asthma	Broad Scope
Blood pressure decreased	Broad Scope
Blood pressure diastolic decreased	Broad Scope
Blood pressure systolic decreased	Broad Scope
Bronchial oedema	Broad Scope
Bronchospasm	Broad Scope
Cardiac arrest	Broad Scope
Cardio-respiratory arrest	Broad Scope
Cardio-respiratory distress	Broad Scope
Cardiovascular insufficiency	Broad Scope
Chest discomfort	Broad Scope
Choking	Broad Scope
Choking sensation	Broad Scope
Circulatory collapse	Narrow Scope
Circumoral oedema	Broad Scope
Cough	Broad Scope
Cyanosis	Broad Scope
Diastolic hypotension	Broad Scope
Dyspnoea	Broad Scope
Erythema	Broad Scope
Eye oedema	Broad Scope
Eye pruritus	Broad Scope
Eye swelling	Broad Scope
Eyelid oedema	Broad Scope
Face oedema	Broad Scope
First use syndrome	Narrow Scope
Flushing	Broad Scope

**Preferred Terms Included in the MedDRA Anaphylactic Reaction SMQ - Broad and Narrow Scopes**

Preferred Term	Term Scope a
Generalised erythema	Broad Scope
Hyperventilation	Broad Scope
Hypotension	Broad Scope
Injection site urticaria	Broad Scope
Kounis syndrome	Narrow Scope
Laryngeal dyspnoea	Broad Scope
Laryngeal oedema	Broad Scope
Laryngospasm	Broad Scope
Laryngotracheal oedema	Broad Scope
Lip oedema	Broad Scope
Lip swelling	Broad Scope
Mouth swelling	Broad Scope
Nasal obstruction	Broad Scope
Ocular hyperaemia	Broad Scope
Oedema	Broad Scope
Oedema mouth	Broad Scope
Oropharyngeal spasm	Broad Scope
Oropharyngeal swelling	Broad Scope
Periorbital oedema	Broad Scope
Pruritus	Broad Scope
Pruritus allergic	Broad Scope
Pruritus generalised	Broad Scope
Rash	Broad Scope
Rash erythematous	Broad Scope
Rash generalised	Broad Scope
Rash pruritic	Broad Scope
Respiratory arrest	Broad Scope
Respiratory distress	Broad Scope
Respiratory failure	Broad Scope
Reversible airways obstruction	Broad Scope
Sensation of foreign body	Broad Scope
Shock	Narrow Scope
Skin swelling	Broad Scope
Sneezing	Broad Scope
Stridor	Broad Scope
Swelling	Broad Scope

## Preferred Terms Included in the MedDRA Anaphylactic Reaction SMQ - Broad and Narrow Scopes

Preferred Term	Term Scope a
Swelling face	Broad Scope
Swollen tongue	Broad Scope
Tachypnoea	Broad Scope
Throat tightness	Broad Scope
Tongue oedema	Broad Scope
Tracheal obstruction	Broad Scope
Tracheal oedema	Broad Scope
Type I hypersensitivity	Narrow Scope
Upper airway obstruction	Broad Scope
Urticaria	Broad Scope
Urticaria papular	Broad Scope
Wheezing	Broad Scope

a All Narrow Scope PTs are also included in the Broad Scope.

MedDRA version 18.0

**APPENDIX 6 STATISTICAL METHODOLOGY****STATISTICAL DETAILS FOR BAYESIAN LOGISTIC REGRESSION MODEL (BLRM AND BLRM-COPULA) AND PRIORS FOR DOSE ESCALATION****1 MODEL SETUP FOR BMS-986016 IN COMBINATION WITH NIVOLUMAB****1.1 Methodology Description for Combination Therapy**

Toxicity profiles of BMS-986016 and nivolumab monotherapies will be incorporated to develop the BMS-986016 and nivolumab combination therapy model framework. A copula-type model will be utilized to cover all general combination cases, including subadditive, additive, and synergistic effects. The combination of the 2 treatments will be explored using a Bayesian hierarchical model by utilizing the toxicity profiles of each monotherapy as prior marginal profiles for the combination. The following copula-type model will be used to describe the probability  $p_{ij}$  of toxicity when dose level  $i$  of treatment A and dose level  $j$  of treatment B are administered in combination:

$$p_{ij} = 1 - \exp \left( - \left[ \{-\log(1 - p_i^m)\}^{1/r} + \{-\log(1 - q_j^n)\}^{1/r} \right]^r \right)$$

Where  $p_i$  is the pre-specified best guess toxicity probability for treatment A and  $q_j$  is the pre-specified best guess toxicity probability for treatment B. Here  $m$  and  $n$  characterize the individual drug effect and  $r$  characterizes drug-drug interactive effect.

The joint toxicity framework models the toxicity rates of all 2 treatments as well as their interaction effects in a multi-parameter hierarchical model, where each of the monotherapy dose-toxicity relationships will be characterized by a 2-parameter BLRM model.

For example, the dose-toxicity relationship for BMS-986016 alone is assumed to follow a logistic model:

$$\text{logit}(p_i) = \log(\alpha_1) + \beta_1 \log \left( \frac{d_{1i}}{d_1^*} \right)$$

where  $p_i$  is the probability of toxicity at dose level  $d_{1i}$ . Note that the  $\alpha_1$  and  $\beta_1$  parameters are assumed positive, and  $d_1^*$  is the reference dose for BMS-986016 ( $\alpha_1$  and  $\beta_1$  are defined in Section 1.2.1).

There are 3 additional parameters for the copula-type model, 1 for each treatment ( $m$  and  $n$ ) as well as 1 for the interaction term ( $r$ ). A dose-toxicity surface will be characterized for different dose combinations of these 2 treatments.

As there are currently no historical data or prior knowledge to indicate how much information to be borrowed for each of the single treatments, parameters  $m$  and  $n$  are all set to be 1, meaning borrowing 100% of the information from all 3 treatments. The above formula is then simplified into a 5-parameter model as follows:

$$p_{ij} = 1 - \exp \left( - \left[ \{-\log(1 - p_i)\}^{1/r} + \{-\log(1 - q_j)\}^{1/r} \right]^r \right)$$

Posteriors for the corresponding 5 parameters (2 logistic regression parameters [ $\alpha_1, \beta_1$ ] for BMS-986016, 2 logistic regression parameters for nivolumab [ $\alpha_2, \beta_2$ ], and 1 interaction parameter for the copula-type model [ $\gamma$ , see details in Section 1.2]) will be fit into the in-house developed model, which implements the above described theoretical setup.

